PACU clinicians are responsible for several clinical and organizational tasks⁵ including patient monitoring and treatment, promoting patient throughput, conducting hand-offs to and from the PACU, and documenting patient care information during the recovery period. As a result, PACU nurses and doctors can feel overwhelmed, and may not always be able to treat symptoms adequately, diagnose physiological derangements accurately, and detect patient deterioration expeditiously. Furthermore, in this high-pressure, high-turnover environment, communication among clinicians is often compromised, resulting in unreliable care coordination. Patient

satisfaction with PACU care varies, as the recognition and prompt treatment of symptoms depends on the availability of assigned clinicians.

The necessity of operating room throughput creates a constant pressure on PACU clinicians to discharge patients rapidly, sometimes before they have recovered sufficiently. This workflow pressure can potentially compromise quality of care and patient safety. Nurses provide the majority of PACU care, typically for no more than two patients at a time during the initial phase of PACU care, in accordance with the American Society of PeriAnesthesia Nurses (ASPN) guidelines⁶. Furthermore, physicians with competing responsibilities often provide oversight in the PACU. For example, a physician who has responsibility for patient assessment and management in the PACU is often simultaneously overseeing anesthetic care in operating rooms or other procedural suites. Surgical clinicians also participate in aspects of PACU care, but are often simultaneously engaged in surgical care of other patients. In addition, the coverage and oversight models can vary considerably across different PACUs, and even within the same PACU over the course of a single day. This is in stark contrast to other high acuity patient care settings, such as operating rooms and intensive care units, where roles and responsibilities of various clinicians are well defined, and staffing models are established.

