This proof-of-concept study has been reviewed and granted a waiver of informed consent for all subjects enrolled by the Human Research Protection Office at Washington University in St. Louis (HRPO#201901180) and is registered at clinicaltrials.gov (NCT04020887). It is infeasible to conduct this proof-of-concept study without a waiver of consent. Additionally, this study has been determined to involve no more than minimal risk to participants, as study participation would not deviate from or delay current standards of peri-anesthesia care. Both the “Good ReseArch for Comparative Effectiveness” (GRACE) checklist⁷ and PICOTS framework⁸ (Table 1) were used in designing this study.

The conduct and reporting of this observational study will follow the “Reporting of studies Conducted using Observational Routinely-collected health Data” (RECORD)⁹ statement and the “Strengthening the Reporting of Observational Studies in Epidemiology” (STROBE)¹⁰ statement guidelines for reporting observational studies.

[figure not shown]
Table 1. PICOTS Framework

PICOTS typology for a comparative effectiveness research protocol	
Population	Adult (18 years and older) patients undergoing elective surgery
Intervention	Telemedicine center for PACU
Comparator	Current post-anesthesia care unit practice
Outcomes	(i) potential utility, and (ii) acceptability of integrating telemedicine in the post-anesthesia care unit environment
Timing	6-month study duration

Setting	Hospital environment – Barnes-Jewish Hospital, St. Louis, Missouri
---------	--

Primary Intervention: Telemedicine Center for PACU

Two bays in Barnes Jewish Hospital (BJH) in St. Louis, Missouri, will be equipped for telemedicine interaction (Figure 1). Video cameras and monitors have been installed in each of these bays to allow for remote monitoring, as well as two-way video communication during the interaction phase. The telemedicine center is staffed by attending anesthesiologists along with certified registered nurse anesthetists (CRNAs), anesthesiology residents, and student registered nurse anesthetists (SRNAs), and is currently providing evidence-based support to clinicians in the operating rooms.^{11–14}

Two PACU bays located across from nurse's station

High-resolution camera for patient monitoring and communication

Ultra-sharp monitor on telescoping arm for two-way patient communication

High-definition microphone for patient monitoring and communication

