Figure 1. Image of post-anesthesia care unit bay in Barnes-Jewish Hospital with two-way video communication.

A station in our telemedicine center will be designated for monitoring patients assigned to the two PACU bays during this proof-of-concept study. Patient information flows to the telemedicine center through the electronic health record (EHR), physiological waveform tracings, and direct video observation. A version of AlertWatch® (AlertWatch, Ann Arbor, Michigan) decision-support software, customized for the PACU environment (Figure 2), will assist clinicians in the telemedicine center in performing core PACU-related functions remotely (see *Aim 1*).

[figure not shown]

Figure 2. AlertWatch® decision-support software, customized for the PACU environment.

Aim 1 – Demonstrate the potential utility of a telemedicine center for the PACU, to assist with PACU functions

The assessments in relation to PACU functions will include:

- 1a. Detection of physiological derangements in PACU patients
- 1b. Identification of symptoms requiring treatment in PACU patients
- 1c. Recognition of situations requiring emergency medical intervention
- 1d. Determination of patient readiness for PACU discharge
- 1e. Participate meaningfully in hand-off activities

Observation Phase (3 months)

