In the first three months (the Observation phase) of this proof-of-concept study, a telemedicine center for the PACU will monitor patients assigned to two PACU bays. Both the telemedicine center and nurses caring for patients in the PACU bays will separately document physiological derangements (Table 2), treatable symptoms (Table 3), or a situation requiring urgent medical intervention (telemedicine center only; Table 4) during the PACU stay. Clinicians in the telemedicine center will assess when the patient meets discharge criteria, based on the modified Aldrete scale¹⁵ and their clinical judgment. They will document the time that discharge criteria are met, the modified Aldrete scale score at this time, and any additional relevant information. If clinicians in the telemedicine center judge that they are unable to determine a patient's readiness for discharge, they will document their reasons (Table 5). Clinical judgment will be used in determining appropriate discharge parameters for patients with pre-existing conditions. The telemedicine center clinicians will document each patient's information outlined in Tables 2-5 directly into REDCapTM (a secure web application for managing online surveys and databases) and AlertWatch. After a patient has been discharged from the PACU, the PACU nurse will fill out a form providing information outlined in Tables 2-5. This includes

information on physiological derangements, treatable symptoms, and discharge information. This form will be collected by the research team, and the information in the form will be documented in REDCap. During this phase of the study, clinicians in the telemedicine center will not communicate with clinicians in the PACU (nurses or physicians), unless there is a patient safety event.

Table 2. Physiological derangements and complications

Did the patient have any of the following physiological derangements:	Definition: (for study purposes)
Persistent confusion / delirium	
Tachycardia	HR >120/min
Bradycardia	HR <45/min
New onset atrial fibrillation	
Respiratory depression	<8 respirations per minute
Hypoxemia	<90% O ₂ Saturation
Hypotension	MAP <55
Weakness	<5/5 power in limbs
Emesis / vomiting	
Hyperglycemia	Glucose >200mg/dL
Hypothermia	Temperature < 35.5 C
Low urine output (for PACU stay >4h)	<0.5 ml/kg per hour

Table 3. Symptoms requiring treatment

Did the patient complain of the following symptoms:	
Dizziness or lightheadedness	Difficulty breathing
Nausea	Shivering

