Physiological derangements – Success will be measured (in the observation phase) by the ability of the telemedicine center clinicians to identify physiological derangements as they are occurring in the PACU. The extent to which the telemedicine center clinicians can identify these physiological derangements will be measured by comparing PACU nurse and telemedicine center assessment surveys for each patient (Figure 3).

Symptom identification and management – Success will be measured (in the observation phase) by the ability of the telemedicine center clinicians to identify treatable symptoms as they arise in the PACU. The extent to which the telemedicine center clinicians can identify these treatable symptoms will be measured by comparing PACU nurse and telemedicine center assessment surveys for each patient (Figure 3).

Emergency situations – Success will be measured (in the observation phase) by the ability of the telemedicine center clinicians to identify situations requiring emergency medical intervention as they are occurring in the PACU. By construction, any time the telemedicine center feels that an emergency situation is present, preserving patient safety mandates contacting the bedside clinician.

During each such contact, the telemedicine center clinician will ask if the PACU nurse was already aware of the situation, disagreed with the assessment, and had already spoken to the supervising physician regarding it. The occurrence of emergency medical situations will be extracted from the electronic health record, and the agreement between telemedicine center and PACU nurse assessments will be quantitated.

PACU discharge – Success will be measured by the ability of the telemedicine center clinicians to identify when patients are ready for discharge (observation phase [without communication] and interaction phase [active communication with patient and PACU clinicians]) (Figure 3). The impact of the telemedicine center on this key function will be examined based on feedback from key stakeholder focus groups (interaction phase; see *Aim 2*). The difference between sign-out times in the observation and the interaction phases will be compared.

Data collection methods and measures during the interaction phase

Aim 1: Demonstrate the potential utility of a telemedicine center for the PACU, to assist with PACU functions

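### Observation-phase agreement between nurse and telemedicine reports may partly reflect telemedicine reading the nurse's chart entries, and the planned tables cannot show how much

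*Combined protocol and SAP*

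**What the plan says.** Under *Observation Phase (3 months)*, telemedicine clinicians and bedside nurses "will separately document physiological derangements" (Table 2) and treatable symptoms (Table 3). One rule keeps the two sides apart: "clinicians in the telemedicine center will not communicate with clinicians in the PACU (nurses or physicians), unless there is a patient safety event". Telemedicine enters its items in REDCap and AlertWatch. The nurse's study report comes later: "After a patient has been discharged from the PACU, the PACU nurse will fill out a form".

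The success measures stand at the end of *Interaction Phase (3 months)* but are labelled as observation-phase measures. Success on derangements is judged "by the ability of the telemedicine center clinicians to identify physiological derangements as they are occurring in the PACU", and its extent "will be measured by comparing PACU nurse and telemedicine center assessment surveys for each patient". The symptom paragraph uses the same comparison. *Secondary Outcomes* reduces each assessment type to present or absent, shows a confusion matrix and summarises it with a Jaccard index.

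On what telemedicine can see, *Primary Intervention: Telemedicine Center for PACU* states: "Patient information flows to the telemedicine center through the electronic health record (EHR), physiological waveform tracings, and direct video observation". The labels to Figure 1 add a "High-definition microphone for patient monitoring and communication". The *Introduction* lists, among the duties of PACU clinicians, "documenting patient care information during the recovery period".

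**The concern.** The success measure reads agreement between two reports as one party's ability to detect events. That reading is safe only if neither party works from the other's findings. Here the telemedicine clinicians have the health record open, and nothing in the protocol hides nursing entries from them or asks them to record an item before looking at the chart.

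Table 3 makes this most pressing, because it asks what the patient complained of. Two-way video and interaction with patients belong to the interaction phase, so in the observation phase telemedicine cannot ask the patient. A nurse's chart entry is then one plausible way to learn of nausea, itching or a pain score above 7.

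*Secondary Outcomes* places at the core of the proposal the belief that telemedicine will find abnormalities that the bedside team missed or found later. High agreement produced partly by chart reading would look like evidence of remote detection without being so. It would also carry over into the case for the larger studies that the protocol foresees.

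**Working it through.** The plan gives no expected agreement, threshold or sample size for this comparison, so there is no stated figure to reproduce. The check has two parts: what the text separates, and what the statistic can separate.

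**What the text separates**
- Channels open to telemedicine: health record, waveforms, video and a bay microphone. The health record is not restricted by phase.
- Barred in the observation phase: communication between clinicians. Chart access is not mentioned.
- The nurse's study form is completed after discharge, so telemedicine cannot copy the form. It could see chart entries made earlier.
- That nurses chart these items in the health record during the stay is an inference from the *Introduction* and *Secondary Outcomes*; it is not stated.
- *Secondary Outcomes* says that the time of nurse detection cannot be reliably determined. The order of the two findings therefore cannot show which route was used.
- Table 4, for emergencies, does record whether the nurse already knew. Tables 2 and 3 have no counterpart.

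**What the statistic separates**

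Let p be the nurse-reported rate, s the share of nurse-reported events that telemedicine detects without the chart, c the share of the remaining nurse-reported events picked up from the chart, and e the telemedicine-only rate among nurse-negative patients. Then

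J = p[s + (1 − s)c] / [p + (1 − p)e].

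Chart pick-up moves patients from the nurse-only cell to the both cell and leaves the denominator alone, so in this model it can only raise J. The model assumes that what the nurse charted and what the nurse ticks on the form agree. None of p, s, c or e is in the documents; all values below are assumed.

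Take p = 0.20, e = 0.05 and the planned 250 patients per phase (*Study Size*). There are 0.20 × 250 = 50 nurse-positive patients and 0.05 × 200 = 10 telemedicine-only patients.
- s = 0.8, c = 0: both = 50 × 0.8 = 40
- s = 0.6, c = 0.5: both = 50 × (0.6 + 0.4 × 0.5) = 40
- s = 0.2, c = 0.75: both = 50 × (0.2 + 0.8 × 0.75) = 40
- s = 0, c = 0.8: both = 50 × 0.8 = 40

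All four give the same table (40 both, 10 nurse only, 10 telemedicine only, 190 neither) and J = 40/60 = 0.667. Own detection of 80% and own detection of nil cannot be told apart.

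With the same p and e, and s = 0.3, J is 0.25 at c = 0, 0.54 at c = 0.5, 0.72 at c = 0.8 and 0.83 at c = 1. With s = 0 and c = 1, J lies between 0.51 and 1.00 over p from 0.05 to 0.40 and e from 0 to 0.05; without chart reading it would be 0.

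In small counts: the nurse reports 20 events, and telemedicine finds 8 of them plus 4 others. J = 8/(20 + 12 − 8) = 8/24 = 0.33. If 10 more are taken from the chart, J = 18/(20 + 22 − 18) = 18/24 = 0.75.

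**The case against.** The other side has real weight.

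- **Late charting.** *Secondary Outcomes* says that nurses may document an abnormality much later if it needs no immediate action. Entries made after telemedicine has recorded an item cannot be copied.
- **Other routes.** The microphone can pick up spoken complaints, shivering and vomiting can be seen on video, and heart rate and saturation should show on the tracings. Exposure differs by item and is small for monitored signs.
- **Chart review is part of the service.** The health record is one of the channels that define it, and Aims 1a and 1b do not say that detection must happen without the chart. Overall agreement is a fair description of the service as delivered.
- **Modest claims.** The plan calls the bedside assessment a limited gold standard, disclaims any superiority test and sets no threshold. No pass/fail decision hangs on the index.
- **The forms are not in the documents.** Only the protocol's description can be said to lack a source field.

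All of this stands, and it narrows the point to non-monitored items and to interpretation. It does not remove it: the success paragraphs still equate agreement with ability to identify events, and neither *Secondary Outcomes* nor *Methodological strengths and limitations* mentions the shared record. An imperfect reference standard, which the plan does admit, is a different problem.

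A reader might infer that the plan claims independent detection, that telemedicine watches nurse charting live, or that agreement will be mere transcription. The documents support none of these. They say the reports are made separately, never independently; they do not describe live charting; and they give no figure for how often an item would be learned from the chart.

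**Conclusion.** The point holds in a limited form. Observation-phase agreement on Tables 2 and 3 may include events that telemedicine learned from the nurse's own entries, and the planned yes/no tables and Jaccard indices cannot show what share. Within the model used here the bias is upward.

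The risk is greatest for severe pain score, nausea, itching, dizziness, limb power, glucose, temperature and urine output. It is lower for monitored signs, and the microphone and late charting reduce it further. The conclusion rests on the inference that nurses chart at least some of these items in the health record during the stay.

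The size is unknown. The step from 0.33 to 0.75 shows that inflation is possible and should not be read as an estimate. The outcome is secondary and descriptive, and the primary outcome of time to discharge readiness is untouched. This is a cheap improvement to an otherwise usable description, and nothing here invalidates the aim.

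**What to change.** 1. Add one source field per Table 2 and Table 3 item to the telemedicine REDCap form: video/audio, waveform/monitor, AlertWatch, or nursing entry, marking where the item was first learned.
2. Keep the planned confusion matrices and Jaccard indices as the description of the service as delivered.
3. Add a second set in which items first learned from a nursing entry are recoded as not detected by telemedicine, with those patients kept in the table. This rule must be fixed in advance. In the small-count example, recoding the 10 chart-learned events leaves 8 both, 12 nurse only and 4 telemedicine only, so 8/24 = 0.33. Dropping them leaves 8, 2 and 4, so 8/14 = 0.57.
4. Name the shared record under *Methodological strengths and limitations*. If the form can no longer be changed, this step alone is still worth taking.

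The cost is one electronic field, a few seconds per entry and some misattribution of source. The recoded index is a conservative, lower figure, because telemedicine might have detected some chart-learned items anyway; the two sets should be reported side by side. Access to the health record and patient care are unchanged. The source cannot be reliably reconstructed afterwards, so the field has to be in place before data collection.

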Severe pain (Numerical Rating Scale >7/10)	Itching
Chest pain unrelated to surgery	

Table 4. Emergency medical interventions

Did the telemedicine center contact PACU clinicians for any of the following interventions:	
Intubation	Unplanned transfusion
Assisted ventilation	Naloxone administration
Cardiopulmonary resuscitation	Return to OR
Cardioversion	Other (free text box)
If Yes, please check all that apply:	
 PACU nurse already aware of the situation	
 PACU nurse unaware of the situation	
 PACU nurse disagreed with the assessment	
 PACU nurse had already spoken to the supervising physician regarding the situation	

Other (please describe):

*Only the telemedicine center will document the detection of urgent situations.

Table 5. Patient discharge readiness

At what time did the patient sufficiently recover to be discharged (case attending anesthesiologist contacted for discharge)?	
PACU Nurses	Telemedicine Center for PACU
Time anesthesiologist is contacted for discharge evaluation	Time ready for discharge
Aldrete Score at discharge	Aldrete Score at discharge
	Unable to determine patient's readiness for discharge
Modified Aldrete Scale Component and Scoring Parameters	If Unable to fully assess, select reason(s) why (Checkbox)
Respiration	 More patient information needed  Equipment issues  Patient cooperation  Other (free text box)
2 – Able to take deep breath and cough	
1 – Dyspnea / Shallow Breathing	
0 – Apnea	
O₂ Saturation	
2 – Maintains > 92% on room air	
1 – Needs O ₂ inhalation to maintain O ₂ saturation > 90%	
0 – Saturation <90% even with supplemental O ₂	
Consciousness	
2 – Fully awake	
1 – Arousable on calling	
0 – Not responding	
Circulation	
2 – BP ± 20mmHg pre-op	
1 – BP ± 20-50mmHg pre-op	
0 – BP ± greater than 50mmHg pre-op	
Motor Activity	
2 – Able to move 4 extremities voluntarily or on command	
1 – Able to move 2 extremities voluntarily or on command	
0 – Able to move 0 extremities voluntarily or on command	

Interaction Phase (3 months)

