The accuracy of physiologic, symptom, and status assessments is less straightforward to analyze. At the heart of the proposal is the belief that telemedicine assistance will detect some abnormalities not caught (or caught later) by the bedside team and detect that the patient has adequate status for PACU discharge before the bedside nurse. Using the bedside assessment as a gold standard is therefore limited. Similarly, although we believe that abnormalities detected by either bedside or telemedicine are unlikely to be false positives, we have no way of assuring that. We also cannot reliably determine the timing of the bedside nurse's detection of an abnormality, as they may document it much later if they believe it does not require an immediate intervention.

Each status assessment event can occur multiple times for each patient; however, we are unlikely to accurately capture the bedside nurse's impression of the number of times an event occurred. We will therefore binarize the presence of each assessment type and display confusion matrices (count tabulations) for each assessment type, which we will summarize with Jaccard indices. The "null hypothesis" that these measures do not agree at all is not meaningful or the subject of this study. As described above, neither is a directional superiority hypothesis possible to evaluate. Final Aldrete scores will be assessed with pearson correlation, and a t-test of the difference in scores presented. Differences in ready-for-discharge times will be summarized as mean and standard deviation, with the null hypothesis of zero mean tested by t-test with a robust standard error.

Agreement of emergency medical status is unlikely to have enough events to be statistically compared. We will present cross-tabulations of (emergency detected by telemedicine center:

yes/no) and (PACU nurse: disagree, investigate and agree, already aware, physician contacted). The absolute rate of telemedicine center false positives (team disagrees), true positives (team unaware), true positives (team aware), and false negatives (team aware > 15 minutes prior or t never detects) will be presented with 95% confidence intervals.

Data Collection

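### The nurse and telemedicine Aldrete scores are not tied to one time, so their difference mixes patient change with rater disagreement

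*Combined protocol and SAP*

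**What the plan says.** Three places in the combined protocol and SAP bear on when the Aldrete score is taken.

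- **Observation Phase, narrative.** The telemedicine score belongs to the moment at which telemedicine judges the patient ready: "They will document the time that discharge criteria are met, the modified Aldrete scale score at this time". For the nurse: "After a patient has been discharged from the PACU, the PACU nurse will fill out a form providing information outlined in Tables 2-5".
- **Table 5.** The nurse column and the telemedicine column carry the same label, "Aldrete Score at discharge". The time fields differ. The telemedicine field is the time the patient is ready. The nurse's field is "Time anesthesiologist is contacted for discharge evaluation".
- **Statistical Methods, Secondary Outcomes.** "Final Aldrete scores will be assessed with pearson correlation, and a t-test of the difference in scores presented". The word for final is not defined. The next sentence handles the times separately: "Differences in ready-for-discharge times will be summarized as mean and standard deviation, with the null hypothesis of zero mean tested by t-test".

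Two further statements matter. The Observation Phase text also restricts contact: "clinicians in the telemedicine center will not communicate with clinicians in the PACU (nurses or physicians), unless there is a patient safety event". Nothing therefore brings the two assessments to the same moment. Secondary Outcomes also states the belief that telemedicine will "detect that the patient has adequate status for PACU discharge before the bedside nurse".

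Nowhere does the plan set a common scoring time, ask for a repeat telemedicine score, or link the score comparison to the time gap.

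**The concern.** The score comparison sits in the part of Secondary Outcomes that deals with the accuracy of physiologic, symptom and status assessments. A reader will therefore take a non-zero mean difference as a sign that the two raters score differently. On the narrative text, however, the telemedicine score may be taken earlier in recovery than the nurse's. A patient who improves in between contributes a difference even when neither rater is biased.

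This works against the study's own aim. The earlier telemedicine correctly recognizes readiness (Aim 1d), the more time there is for its score to differ from the nurse's, so success on timing could look like poor scoring.

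The correlation is exposed too, because patients do not all change by the same amount in the gap. That is separate from whether a correlation is a suitable measure of agreement.

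**Working it through.** **The plan's own figure.** No power or precision is stated for the Aldrete comparison. The only power statement concerns the primary outcome, and it reproduces. With SD 65 and 250 per phase, SE = 65 × √(2/250) = 5.81 min. A 20 min difference then gives two-sided power of 93.1% at alpha 0.05 and 73.7% at alpha 0.005, in line with the stated >90% and >70%. It does not bear on this point.

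**What the difference estimates.** For one patient, let telemedicine score at time t1 and the nurse at time t2.

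E(nurse − telemedicine) = rater bias + mean change in the patient from t1 to t2

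If t1 = t2 the second term is zero. The plan does not require that, and it expects t1 before t2. The t-test sees only the sum.

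**Inputs for an illustration.**
- Pairs: n = 250, from the planned observation-phase size. This is a maximum, because Table 5 lets telemedicine record that readiness could not be determined.
- Two-sided alpha 0.05 (assumed).
- Rater bias: zero (assumed).
- Mean gain 0.1 or 0.2 points, and difference SD 0.7 or 1.0. All are assumptions. The SD contains random rater error as well as patient change.

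**Formula.** SE = SD/√n. P(reject) = Φ(gain/SE − 1.96) + Φ(−gain/SE − 1.96).

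| Difference SD | SE | Gain 0 | Gain 0.1 | Gain 0.2 |
|---|---|---|---|---|
| 0.7 | 0.7/√250 = 0.044 | 5% | 0.1/0.0443 = 2.26 → 62% | 99% |
| 1.0 | 1.0/√250 = 0.063 | 5% | 0.1/0.0632 = 1.58 → 35% | 89% |

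**Does the ceiling at 10 remove the effect?** A simulation used 250 patients with assumed true scores of 8, 9 and 10 in 10%, 40% and 50%. Rater error was symmetric, one point up or down, and scores were capped at 10. A given share of patients gained one point in the gap, unless already at 10.

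| Share gaining | Rejection, 5% error per rater | Rejection, 20% error per rater |
|---|---|---|
| 0% | 0.05 | 0.05 |
| 5% | 0.23 | 0.10 |
| 10% | 0.61 | 0.25 |
| 20% | 0.98 | 0.68 |

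As the share rises from 0% to 20%, the mean Pearson correlation falls from 0.92 to 0.82 (5% error) and from 0.72 to 0.65 (20% error). The ceiling shrinks the mean shift (about 0.05 points when 10% gain) but does not remove the effect.

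**The case against.** **The plan may mean something else.** It says only that the test will be presented, not that it isolates rater disagreement. Table 5 puts both columns under one question about when the patient had recovered enough. One could therefore read each score as the one at that rater's own readiness call, so that different times are part of what is compared. Or, on the table's labels, both scores are at discharge and the gap largely disappears. Neither reading survives the whole text. The first conflicts with the at-discharge label and the accuracy framing, and the second conflicts with the narrative rule for telemedicine. What stands is that the passages disagree about when an analyzed variable is measured.

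**The late form proves little.** This is correct. Completing the form after discharge shows when the nurse's score is recorded, not when the patient was scored.

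**The gap will be visible.** The plan reports the difference in readiness times next to the score comparison and admits that the bedside assessment is a limited standard. That helps a careful reader, but it does not adjust the score test.

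**A stronger reading that a reader might infer** is that the test will report telemedicine under-scoring even between raters in perfect agreement, at the rates tabulated above. The documents do not support this, for three reasons.
- Earlier telemedicine detection is stated as a belief, and scores can also fall in the gap, so the direction is only expected.
- Perfect agreement does not fit the SDs used. With one-point changes only, mean 0.1 and SD 0.7 give E(d²) = 0.49 + 0.01 = 0.50, so 30% of patients would improve and 20% worsen. SD 1.0 gives 1.01, which is impossible. If 10% gain a point and nobody else changes, SD = √(0.1 × 0.9) = 0.30 and rejection exceeds 99%. The 62% and 35% therefore assume no systematic bias with random error present. They are neither an estimate nor a bound.
- The plan commits to no conclusion of under-scoring.

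**Conclusion.** The point holds as a matter of definition. The Observation Phase text, Table 5 and Secondary Outcomes do not fix one scoring time, and the planned comparison of final scores cannot separate rater bias from patient change. That conclusion needs no numerical assumption.

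The size cannot be obtained from the documents. Small shifts could matter with up to 250 pairs, but the rejection rate depends almost entirely on the assumed gain and SD. The simulated rates with some gain run from 0.10 to 0.98.

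The point is minor. It concerns one secondary analysis for which no power is claimed. A reader might infer that the primary outcome or the sample size is undermined, but neither uses the Aldrete score difference.

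**What to change.** - **Name one time.** Reconcile the Observation Phase text, Table 5 and Secondary Outcomes so that both raters' scores for this comparison refer to the same stated moment, and define final accordingly. Departure from the bay is one option, in keeping with Table 5's label. The nurse's form must state the same moment.
- **Add one score.** Telemedicine keeps its criteria-met score and records a second at the common time, blind to the nurse's, from the video, EHR and monitor feeds it already has.
- **Analyze the same-time pair.** Keep the criteria-met score for describing the patient's state when telemedicine called readiness.
- **Matching on charted scores.** Comparing the criteria-met score with the nurse-charted score nearest in time is possible only if nurses chart serial Aldrete scores, which the documents do not say.
- **If no second score is added.** Present the score difference together with the time gap, and state that it is not a measure of rater disagreement.

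The cost is one extra score per patient by a clinician already watching. It has to be set up before data collection, because a score that was never recorded cannot be recovered. The drawback is that scores at departure will cluster nearer the maximum, which leaves less variation for an agreement analysis.
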